6.1.1 Treatment Groups

Findings collected up to Week 24 visit will be analyzed by treatment groups based on the treatments that subjects take in Part I of the study:

- Placebo
- AS012
- AS012
- AS012
- AS012

Findings collected after Week 24 visit (including those in the follow-up part of the study) will be analyzed by treatment groups based on the treatments that subjects take in Part II of the study:

- Placebo/AS012
- Placebo/AS012
- AS012
- AS012
- AS012
- AS012

Note that subjects initially randomized to Placebo and re-randomized to AS012 doses after Week 24 will not be pooled with subjects taking the same doses from the study start due to different exposure times.

Adverse events will be analyzed by actual treatment at the time of event onset, i.e., using the same treatment groups as findings collected up to Week 24.

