6.11.1 Adverse Events

Adverse Events will be coded using the MedDRA (Version 23.1) AE coding system for purposes of summarization.

[figure not shown]
An AE will be considered as treatment-emergent (TEAE) if the date of onset is on or after the date of the first study drug administration. AEs with unknown start dates will be counted as treatment-emergent unless the AE resolution date is prior to the study drug start date. If the start date is partially missing, the AE will be considered treatment-emergent, unless the month and year (when available) rule out the possibility that the event occurred post start of study drug dosing.

A TEAE is defined as treatment-related if its relationship to study medication is recorded as "Possible", "Probable" or "Definite" on the eCRF. In case the relatedness was not assessed, the most conservative result (related) will be chosen for the analysis.

For subjects initially randomized to Placebo and later re-randomized to AS012 AEs will be assigned to either Placebo or AS012 treatment based on the date of onset, i.e., AEs that start prior to the first dose of AS012 will be assigned to the Placebo treatment and AEs that start on or after the date of the first AS012 dose will be assigned to the AS012 treatment.

TEAEs will be defined as occurring in Part I of the study if the date of onset is prior to the date of the subject's Week 24 visit. For subjects who discontinue prior to Week 24 visits, all their TEAEs will be defined as occurring in Part I. AEs starting on or after the date of the subject's Week 24 visit will be defined as occurring after Part I.

All summaries of TEAEs will be presented in three ways:

In summaries of TEAEs a subject experiencing the same AE multiple times on the same treatment will only be counted once for that preferred term and treatment. Similarly, if a subject experiences multiple AEs within the same system organ class on the same treatment that subject will be counted only once in that system organ class and treatment. When summarizing AEs by severity, only the most severe occurrence within the preferred term or system organ class and treatment will be used. Similarly, when summarizing AEs by

relationship to study drug, only the most related occurrence within the preferred term or system organ class and treatment will be selected for displays in summary tables.

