An overall summary for the Safety population will include, by treatment and overall, the number and percentage of subjects reporting at least 1 TEAE in the following categories:

- Any TEAE
- Treatment-related TEAE
- Serious TEAE
- Treatment-related serious TEAE
- TEAE leading to discontinuation of the study medication
- Treatment-related TEAE leading to discontinuation of the study medication
- TEAE requiring temporary interruption of study medication
- Treatment-related TEAE requiring temporary interruption of study medication
- TEAE leading to death.

The following TEAE frequency tables will be prepared summarizing the overall number of TEAEs, the number and percentage of subjects reporting at least one TEAE by MedDRA System Organ Class (SOC) and preferred term (PT), by treatment group for the Safety population:

- All TEAEs
- Serious TEAEs
- Treatment-related TEAEs
- AEs leading to discontinuation of the study medication
- TEAEs by Severity
- TEAEs by Relationship to Study Drug.

Overall summary of TEAEs and the summary of TEAEs by SOC and PT will be presented separately for TEAEs occurring in Part I, occurring after Part I and for all TEAEs for subjects initially randomized to AS012 treatment.

All information pertaining to AEs noted during the study will be listed by subject, detailing verbatim, preferred term, system organ class, start date, stop date, intensity, outcome, action taken and causal relationship to the study drug. The AE onset will also be shown relative (in number of days) to the date of first administration of the study drug. In addition the AE duration (if AE Stop Date is available) will be evaluated as below and presented (in number of days).

AE Duration = AE Stop Date - AE Start Date + 1

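### The summary of adverse events after Part I combines placebo switchers with subjects on the same AS012 dose since Day 1, in two of the four dose columns only

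*SAP*

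**What the plan says.** SAP 6.1.1 defines two sets of treatment groups. Findings up to the Week 24 visit use five: placebo and four AS012 groups. For the later period, "Findings collected after Week 24 visit (including those in the follow-up part of the study) will be analyzed by treatment groups" of Part II. There are six of these: two Placebo/AS012 groups and four groups that took AS012 throughout. A note adds that the switchers "will not be pooled with subjects taking the same doses from the study start due to different exposure times".

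The next sentence sets a different rule for adverse events: "Adverse events will be analyzed by actual treatment at the time of event onset, i.e., using the same treatment groups". The groups it refers to are those for the period before the switch. That is the five-group layout, with no column for switchers.

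SAP 6.11.1 agrees with it. For subjects re-randomised from placebo, "AEs that start on or after the date of the first AS012 dose will be assigned to the AS012 treatment". The same section says that the overall TEAE summary and the summary by system organ class and preferred term are "presented separately for TEAEs occurring in Part I, occurring after Part I and for all TEAEs for subjects initially randomized to AS012 treatment".

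Protocol 9.7 also plans a summary by the actual dose at onset, and states that safety analyses are not inferential.

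**The concern.** After Week 24, switchers are in roughly weeks 0 to 28 on AS012, while continuing subjects are in weeks 24 to 52. Continuing subjects who could not tolerate the drug may already have left; switchers have had no such selection on active drug. This is the difference in exposure that the SAP gives as its reason for not pooling, and it applies to adverse events as much as to laboratory values, vital signs or ECGs.

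Placebo subjects are re-randomised 1:1 to AS012, so only two of the four doses receive switchers. Any effect of time on drug then falls on two columns and not on the others, and dose is confounded with time on drug. The planned tables give numbers and percentages of subjects, and the visible text has no rate adjusted for exposure that would separate the two. The SAP lists safety of different doses over 52 weeks as a secondary objective, and this is the view that shows late events by dose.

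**Working it through.** **Which summaries are affected**

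- Part I: no switcher is yet on AS012. Not affected.
- All TEAEs in subjects who started on AS012: switchers are excluded. Not affected.
- After Part I: switchers' events fall in the column of their new dose. Affected.

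**Share of switchers in an affected column**

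Inputs: about 320 subjects in five arms and 52 evaluable per arm (SAP 3.2); 1:1 re-randomisation of placebo and the allocation ratios (SAP 3.1; protocol synopsis).

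- The plan's arm size: 320/5 = 64, as stated. The ratio switch after 55% of enrolment (protocol synopsis) also gives 176 × 3/11 + 144 × 1/9 = 48 + 16 = 64.
- Switchers per receiving dose: 64/2 = 32. Share: 32/(32 + 64) = 33%.
- At 52 evaluable per arm: 26/(26 + 52) = 33%.
- With the switch after 45% (SAP 3.1): placebo and the other arms with the same ratio have 144 × 3/11 + 176 × 1/9 = 58.8; the remaining arms have 144 × 1/11 + 176 × 3/9 = 71.8. The share is 29.4/(29.4 + 58.8) = 33% or 29.4/(29.4 + 71.8) = 29%, depending on which doses receive switchers.

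The other two dose columns contain no switchers.

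**Size of a possible artificial gap**

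Let w be the switchers' share, E the event rate in switchers and L the rate in continuing subjects, with E and L the same at every dose. The mixed column shows wE + (1 - w)L and an unmixed column shows L, so the gap is w(E - L). The documents give no adverse event rates, so E and L are assumptions. With L = 20%:

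| E (assumed) | Mixed column, w = 33% | Gap, w = 33% | Gap, w = 29% |
|---|---|---|---|
| 10% | 16.7% | -3.3 points | -2.9 points |
| 20% | 20.0% | 0 | 0 |
| 30% | 23.3% | +3.3 points | +2.9 points |
| 40% | 26.7% | +6.7 points | +5.8 points |
| 50% | 30.0% | +10.0 points | +8.7 points |

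With switchers in their own columns, the gap between continuing-dose columns is zero under the same assumptions.

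**Precision**

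For a 20% rate the standard error is √(0.2 × 0.8/n): 7.1 points at n = 32, 5.0 at n = 64 and 4.1 at n = 96.

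**The case against.** The strongest reply is that this is a deliberate choice. The adverse event rule is a separate, explicit sentence, and SAP 6.11.1 repeats its effect. It also fits protocol 9.7, which requires a summary by actual dose at onset. The SAP likewise counts switchers under both treatments for whole-study exposure (6.8) and for concomitant medication (6.11.6). A reader might infer that the SAP breaks its own rule. The text does not support that: it makes an exception, without giving a reason. Attribution by treatment at onset is sound, and the six-group layout respects it too.

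Two of the three TEAE views are free of the problem, including the placebo-controlled one and the one covering all four doses over the whole study. Safety analysis is descriptive, and all events are listed by subject, so switchers can be separated later. These points limit the consequence. They do not remove it, because neither unaffected view isolates late events by dose, and safety judgements here rest on descriptive tables.

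Both groups are followed over the same calendar period, Week 24 to Week 64, including 12 weeks off drug. Only time since first active dose differs, but that is the quantity at issue.

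SAP 6.11.1 also says "All summaries of TEAEs will be presented in three ways", and the list that follows is not shown in the public copy; the table shells are a separate document. Either could bear on layout. The visible grouping rules are nevertheless clear, and if the shells already separate switchers, 6.1.1 should say so.

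**Conclusion.** The point holds for one table. On the visible text, the after-Part-I TEAE summary places about 32 switchers with about 64 continuing subjects in each of two dose columns (29% to 33% of the column) and none in the other two. This assumes that similar proportions of the placebo and active arms reach Week 24.

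Whether it biases that table depends on how risk changes with time on drug, which the documents do not show. Under the assumed rates the artificial gap runs from -3.3 to +10 points and is zero if risk is constant. A mixed column cannot show which case applies; separate columns can.

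Two stronger readings go too far. One is that the doses receiving switchers will show higher late event rates: that assumes early risk is higher, and the documents contain no such figure. The other is that the trial's dose-safety comparison is lost: the Part I summary and the summary of subjects who started on AS012 remain valid comparisons of the four doses.

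**What to change.** In SAP 6.1.1 and 6.11.1, present TEAEs occurring after Part I in the six Part II groups, with the two Placebo/AS012 columns separate. Keep the summary by actual dose at onset as a supplement, so that the commitment in protocol 9.7 is still met. If the sponsor prefers the combined table as the main one, 6.1.1 should state why adverse events are handled differently from other findings after Week 24.

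The cost is SAP wording and one more table layout, with no new data. The switcher columns will be less precise: for a 20% rate, a standard error of about 7.1 points at n = 32, against 4.1 in a pooled column of 96. The continuing-dose columns, at about 5.0 points with n = 64, lose less and become comparable with one another.

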6.1.2 Adjustment for multiplicity

No adjustment for multiplicity will be needed for the analysis of the primary endpoint due to the step-down testing approach described in Section 6.9.1.2. P-values for other endpoints will be presented nominally, without multiplicity adjustment. No inferences will be drawn from these p-values.

6.2 Subject Disposition

The number of subjects who were screened, were screen failures, were randomized to treatment, included in the Safety, ITT, presented prematurely discontinued from the study (along with the reasons for discontinuation) will be presented.

All disposition information will be listed. Date of completion/discontinuation shown in this listing will be derived as the maximum between then the Date of Completion/Discontinuation collected at the End of Study eCRF and the date of last visit collected at Visit Details eCRF. Also, a listing of enrollment details will provide the date of informed consent and inclusion/exclusion criteria not met, if any.

6.3 Demographic and Baseline Characteristics

Demographic and baseline characteristics will include:

Descriptive statistics will be presented for continuous variables. Frequency counts and percentage will be presented for categorical variables. Height will be presented in centimeters, weight in kilograms, and BMI in kg/m².

Age will be derived from Informed Consent Date and Date of Birth as the number of whole years between those two dates.

These analyses will be performed for the Safety, ITT, populations.

All demographic parameters and baseline characteristics will be presented in the by-subject listings.

6.4 Medical history

Medical history will be summarized by Medical Dictionary of Regulatory Activities (MedDRA) (Version 23.1) System Organ Class and Preferred Term. One subject will be counted once for each applicable Preferred Term and System Organ Class. This summary will be performed for the Safety population. All medical history information will be listed.

6.5 Protocol Deviations

Protocol deviations will be derived algorithmically as well as reported by sites.

Specific

deviations and their exclusion status are defined in the separate Protocol Deviations Specification document.

All classification of

protocol deviations will be performed prior to database lock.

6.6 Chest X-Ray

Before Baseline visit a chest X-ray should be evaluated for concurrent medical condition or uncontrolled, clinically significant systemic disease. A chest X-ray is acceptable if performed within the past 6 months and available at a site along with an associated report. All results from the chest x-ray collected on eCRF will be listed.

6.8 Study Drug Exposure and Compliance

Duration of exposure will be defined as follows:

[Date of Last Dose] – [Date of First Dose] + 1

For subjects initially randomized to AS012, Date of Last Dose is collected at the End of Study eCRF and Date of First Dose is collected at the Study Drug Administration eCRF at Visit 2. In case Date of Last Dose is not collected at the End of Study eCRF (e.g. the subject is lost to follow-up), the date of last dose will be assumed to be equal to the date of the last visit in the study.

Duration of exposure will also be defined separately for Part I of the study and Part II of the study.

For Part I, Date of Last Dose is the date preceding the date of study drug administration at Visit 7/Week 24, provided the subject is administered drug at Visit 7; otherwise, it is the Date

of Last Dose as collected at the End of Study eCRF. The Date of First dose is collected at the Study Drug Administration eCRF at Visit 2.

For Part II the Date of Last Dose is collected at the End of Study eCRF and Date of First Dose is collected at the Study Drug Administration eCRF at Visit 7/Week 24.

Compliance will be calculated in terms of total number of tablets taken separately for Part I, Part II and both parts overall. Compliance will be defined in two ways:

- 1. Based on the diary data as (9*[Number of planned treatment days] [Total number of missed tablets]) / (9*[Number of planned treatment days]) *100%
- 2. Based on the drug accountability data as ([Total number of drug bottles dispensed]*105 [Total number of tablets returned])/ (9*[Number of planned treatment days]) *100%. This is based on the assumption that each dispensed bottle contained 105 tablets.

Number of planned treatment days will be defined as follows:

- For Part I
 - For subjects that completed Part I, i.e. attended Week 24 visit: [Date of Week
 24 Visit] [Date of the first dose of the study drug]
 - For subjects that discontinued in Part I: [Date of discontinuation] [Date of the first dose of the study drug] + 1
- For Part II
 - For subjects that completed Part II, i.e. attended Week 52 visit: [Date of Week 52 Visit] [Date of Week 24 Visit] + 1
 - For subjects that discontinued in Part II: [Date of discontinuation] [Date of Week 24 Visit] + 1
- For overall compliance (for subject initially randomized to AS012)
 - For subjects that completed Part II, i.e. attended Week 52 visit: [Date of Week 52 Visit] [Date of the first dose of the study drug] + 1
 - For subjects that discontinued in Part I or Part II: [Date of discontinuation] –
 [Date of the first dose of the study drug] + 1

Total number of missed tablets will be calculated form the diary data by summing up the values "Total Number of Missed Tablets Per Diary (At Morning)", "Total Number of Missed Tablets Per Diary (At Afternoon)" and "Total Number of Missed Tablets Per Diary (At Evening)" transcribed at the "Study Drug Accountability" eCRF across applicable visits, i.e:

- For Part I: visits up to and including Week 24 Visit, including any unscheduled visits occurring before Week 24 Visit date
- For Part II: visits after Week 24 Visit, including any unscheduled visits occurring after Week 24 Visit date
- For overall compliance (for subject initially randomized to AS012); all visits

If the subject did not return the diary at least once and therefore the number of missed tablets is not known, the compliance will not be calculated.

Total number of dispensed bottles and total number of returned tablets will be calculated from the "Study Drug Accountability" eCRF by summing up the appropriate fields across the applicable visits.

For subjects initially randomized to placebo overall compliance will be calculated separately for Placebo treatment in Part I and for AS012 treatment in Part II.

Subject will be defined as non-compliant if the subject missed more than 14 continuous days of treatments. Information on missing more than 14 continuous days of treatments will be derived from the subject diaries by the sites and entered into eCRF.

Duration of exposure and compliance (both definitions) will be summarized descriptively by treatment group for the Safety population, separately for Part I and for the entire study. Number and percentage of non-compliant subjects will also be provided. In the summary for the entire study subjects initially randomized to Placebo in Part I and re-randomized to AS012 in Part II of the study will be summarized under both treatments they received.

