## 5.10 Treatment Interruption Guidance for AEs

The treatment period should not be extended beyond 52 weeks due to missed doses or treatment interruption periods. Subjects whose condition worsens (e.g. an increase in VASI score from baseline by  $\geq 25\%$ , or development of allergic reactions or the development of other potentially serious drug reactions) should be re-evaluated by the Investigator and management reconsidered.

Study drug dosing may be temporarily suspended in the event of:

- Clinically important laboratory abnormalities
- Other inter-current illnesses or major surgery or AE related or unrelated to the study treatment

A decision to discontinue IP and/or to resumption of study treatment after temporary discontinuation due to illness, AE or laboratory abnormality should be discussed with the Medical Monitor. The Investigator may suspend study treatment at any time, without consultation with the medical monitor if the urgency of the situation requires immediate action and if this is determined to be in the subject's best interest. Medical Monitor should be contacted as soon as possible in any case of IP discontinuation.

May 20, 2022 Protocol: **AS012-20-01** Page 29 of 88

The subject shall be discontinued from the study if more than 2 temporary interruptions are needed for these reasons. The maximum allowable duration for each of a temporary discontinuation of the study drug will be 14-day time period.

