# 7.15 Unscheduled Visits and Early Discontinuation Visit

An Unscheduled Visit is allowed at any time, for any reason, if in the Principal Investigator's opinion it is warranted. If the Unscheduled Visit is due to an AE, the Principal Investigator will determine whether additional visits are needed.

If a Subject is discontinued from the study during an Unscheduled Visit, the Unscheduled Visit will be referred to as an Early Discontinuation Visit:

- 1. A urine pregnancy test will be conducted for all females of childbearing potential (see Section 5.4)
- 2. The use of concomitant medications since the previous study visit will be documented and assessed. (See Section 5.6)
- 3. The occurrence of all AEs will be assessed and documented following the procedures in Sections 5.7, 10.1, and 10.3

Additional assessments may be performed per the Investigator's decision.

For all the subjects who discontinue the study prior to Visit 7 all efforts should be made to conduct a visit at, or close to week 24 to collect focused area assessments. Regardless of the reason, Subjects discontinued from IP prior to the end of study will be required to complete the End of Study (EoS) assessment within 2 weeks after the last dose.

If the Subject's condition has worsened to the degree that it is unsafe for the Subject to continue in the study, the Subject may be discontinued from the study as treatment failure and a standard of care treatment may be advised at the Principal Investigator's discretion.

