3. STUDY OVERVIEW

3.1 Study Design

Subjects in this randomized, double-blind, placebo controlled, parallel-group, multiple-center study will be assigned to treatment with the investigational products or placebo control according to a randomization scheme.

- Part I: 24 weeks: Subjects will be randomized to Placebo,
 or AS012 in 3:3:1:3:1 ratio (approximately first 45% of enrolled subjects) or in 1:1:3:1:3 (approximately remaining 55% enrolled subjects).
- Part II: week 24 to week 52: Subjects initially randomized to placebo will be rerandomized to AS012 in 1:1 ratio. Subjects originally randomized to AS012 doses will remain on their assigned dosing regimen until the end of Part II (week 52).
- Part III: week 52 to week 64: After week 52 (or early termination of study treatment prior to week 52), the study treatment will be stopped, and all subjects will enter the follow-up period to monitor safety and tolerability for 12 weeks following last dose of study treatment.

Clinical Evaluations will be performed at:

- Visit 1: Screening Visit (Week \geq -4 / Day -28 to -1);
- Visit 2: Baseline Visit (Week 1 / Day 1);
- Visit 3: Interim Visit (Week 4 / Day 29 ± 3 Days);
- Visit 4: Interim Visit (Week 12 / Day 85 ± 3 Days);
- Visit 5: Interim Visit (Week 16 / Day 113 ± 3 Days);
- Visit 6: Interim Visit (Week 20 / Day 141 ± 3 Days);
- Visit 7: Interim Visit (Week 24 / Day 169 ± 3 Days);
- Visit 8: Interim Visit (Week 28 / Day 197 ± 3 Days);
- Visit 9: Interim Visit (Week $36 / \text{Day } 253 \pm 3 \text{ Days}$);
- Visit 10: Interim Visit (Week 44 / Day 309 ± 3 Days);
- Visit 11: Interim Visit (Week 48 / Day 337 \pm 3 Days);
- Visit 12: End of Treatment Visit (Week 52 / Day 365 ± 3 Days);
- Visit 13: Follow-up Visit (Week 64 / Day 449 \pm 3 Days);

Subjects will be admitted into the study after informed consent has been obtained. An Unscheduled Visit is allowed at any time, for any reason, if in the Principal Investigator's opinion it is warranted. If a subject is discontinued from the study during an Unscheduled Visit, the Unscheduled Visit will be referred to as an Early Discontinuation Visit. Subjects discontinued from Investigational Product (IP) prior to the end of study will be required to complete the End of Study (EoS) assessment within 2 weeks after the last dose.

Randomization and re-randomization will be stratified by stability of disease (stable vs. non-stable)

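### Two date rules in SAP 6.8 give wrong descriptive values for some subjects: Part I exposure can absorb Part II, and off-drug days can enter the compliance denominator

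*SAP*

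**What the plan says.** **Exposure (SAP 6.8).** The Part I last dose is the day before the Visit 7 administration, "provided the subject is administered drug at Visit 7; otherwise, it is the Date" of last dose held on the End of Study eCRF. Nothing limits that second branch to subjects who stopped in Part I. The Part II first dose comes only from the Visit 7 administration record. Overall exposure, defined for subjects first randomized to AS012, ends at the collected last dose, as does Part II exposure.

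**Compliance (SAP 6.8).** Two measures are reported, one from the diary and one from drug accountability, and both divide by 9 times the planned treatment days. For early stoppers the planned days end at the date of discontinuation ("For subjects that discontinued in Part I: [Date of discontinuation" for Part I, "For subjects that discontinued in Part II: [Date of discontinuation" for Part II). Completion is a matter of attendance: "For subjects that completed Part I, i.e. attended Week 24 visit". Part II completion is likewise defined by attending Week 52.

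**Off-drug contact is planned.** Subjects who stop study drug early "will be required to complete the End of Study (EoS) assessment within 2 weeks after the last dose" (SAP 3.1). For those who leave the study before Visit 7, "all efforts should be made to conduct a visit at, or close to week 24" (Protocol 7.15). Interruptions are also foreseen: "Study drug dosing may be temporarily suspended in the event of" several listed events, for at most 14 days each (Protocol 5.10).

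**The concern.** The exposure rule treats absence of a dose at Visit 7 as if it meant that treatment had ended. A subject on a permitted interruption that day who later resumes falls into the same branch. All later dosing is then booked to Part I, and Part II has no start date. For a subject first randomized to placebo, AS012 days become placebo exposure. The overall exposure rule does not rescue this case, because it is written only for subjects first randomized to AS012.

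The compliance rule lets days on which no drug was due count as planned dosing days. An early stopper who returns for Week 24 also fits two bullets at once, completer and discontinuer, and the SAP does not say which takes precedence. The two measures can then disagree widely for the same subject. Because the error grows with early stopping, an arm with more stopping for tolerability could look less adherent in the accountability table.

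**Working it through.** **Inputs from the documents.** Visit 7 is Day 169 and Visit 12 is Day 365 (SAP 3.1). Dosing lasts 365 consecutive days (Protocol 8.6). Three tablets three times a day gives 9 per day (SAP 3.1). The EoS assessment is up to 14 days after the last dose (SAP 3.1). Drop-out is about 20% (SAP 3.2).

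**Assumed, not in the documents.** The last dose is on Day 60, with adherence to that day of either 100% or 80%.

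**1. The plan's own figure.** For a completer on schedule:
- Part I planned days: 169 − 1 = 168
- Part II planned days: 365 − 169 + 1 = 197
- Overall: 365 − 1 + 1 = 365 = 168 + 197

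The formulas return the stated 365 days when everyone follows the schedule.

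**2. Part I exposure, undosed at Visit 7 but continuing.** Duration is last dose − first dose + 1.
- Last dose Day 365: 365 − 1 + 1 = 365 days, which is 365 − 168 = 197 too many
- Last dose Day 253: 253 days, which is 253 − 168 = 85 too many

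In both cases the Part II first dose is undefined. The 168 is nominal; an interruption before Visit 7 would make the true figure somewhat lower.

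**3. Compliance, last dose Day 60.** Full adherence means 60 × 9 = 540 tablets taken. Adherence of 80% means 432 taken and 108 missed. Accountability is taken / (9 × days). Diary is (9 × days − missed) / (9 × days), shown here with no tablets after stopping entered as missed.

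| Planned days end at | Days | Full adherence: accountability | Full adherence: diary | 80% adherence: accountability | 80% adherence: diary |
|---|---|---|---|---|---|
| Last dose | 60 | 540/540 = 100% | 100% | 432/540 = 80.0% | 80.0% |
| Discontinuation 14 days later | 74 | 540/666 = 81.1% | 100% | 432/666 = 64.9% | 558/666 = 83.8% |
| Week 24 visit | 168 | 540/1512 = 35.7% | 100% | 432/1512 = 28.6% | 1404/1512 = 92.9% |

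If tablets after stopping are entered as missed, the diary figure equals the accountability figure in every row.

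**4. Arm mean, illustration only.** Suppose 20% of an arm stop on Day 60, discontinuation is dated 14 days later, and everyone else is at 100%. The accountability mean falls by 0.20 × (100 − 81.1) = 3.8, about 4 points.

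**The case against.** The case against is strong in several places.

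- **The Visit 7 fault is an edge case.** It needs an interruption of at most 14 days to cover a visit at which dosing is supervised (Protocol 8.6), followed by resumption. The branch was evidently meant for subjects who stopped in Part I. This stands as a limit on frequency, but the text does not contain the restriction.
- **Ending planned days at discontinuation can be deliberate.** Protocol 8.6 removes subjects who miss all doses for more than 14 consecutive days. With a last dose on Day 60 and removal on Day 75, the present rule gives 60/75 = 80%. Ending at the last dose would give 100% and hide the very non-adherence that led to removal. This stands, and it shapes the fix.
- **Diary inflation is conditional.** Subjects are told to record all missed doses (Protocol 8.6), and SAP 6.8 calculates no compliance when a diary is not returned and the missed tablets are unknown. It also counts subjects who miss more than 14 continuous days separately. Whether tablets after a permanent stop are entered as missed is not settled.

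Four stronger readings are tempting, and the documents do not support them:

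- **That compliance is overstated in general.** Accountability errs low. Only the diary can err high, and only under the condition above.
- **That exposure generally runs past the last dose.** Overall and Part II exposure end at the collected date, with the last visit used only when that date is missing. The Part I fault crosses the Part I boundary, not the final dose.
- **That SAP 6.2 settles the discontinuation date.** Its rule ("derived as the maximum between then the Date of Completion/Discontinuation collected at the End of Study eCRF and the date of last visit") is stated for the disposition listing, and 6.8 does not invoke it.
- **That the arm mean could fall by 0.20 × 64.3 = 12.9 points.** This applies the Week 24 attender figure to the whole planned drop-out. That 20% describes subjects not evaluable at analysis, whereas a subject assessed at Week 24 is evaluable.

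**Conclusion.** Both rules are wrong as written, on a modest scale. Under the first, each affected subject can have up to 197 days too many in Part I and no Part II exposure; the number of such subjects is unknown and probably small. Under the second, a subject fully adherent to Day 60 can show 81% or 36% by accountability according to how the stop is dated or classified, while the diary may show 100%. The stopping day is an assumption. The 4-point shift in an arm mean further assumes that all stoppers have discontinuation dated at the 14-day limit and that all other subjects are at 100%.

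A reader might infer that the efficacy or adverse-event results are compromised. The documents do not show that. The primary ANCOVA has no exposure or compliance term (SAP 6.9.1.2). The adverse-event tables count subjects and events under their own date rules (SAP 6.11.1), and Protocol 9.7 plans no inferential analysis of exposure. The consequence is confined to the descriptive exposure and compliance tables.

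**What to change.** **Exposure.**
- Limit the fallback to the End of Study last dose to subjects who took no study drug after the Week 24 visit.
- For subjects who continue, end Part I no later than the day before the Week 24 visit or the start of the Part II kit.
- Take the Part II first dose as the first dose from the Visit 7 kit, using the diary date when none is given in clinic.

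**Compliance.**
- Base Part I and Part II completion on being on treatment, not on attendance. A subject who is only interrupted at the visit and later resumes should not be classed as stopped.
- For subjects permanently stopped for reasons other than non-compliance, end planned days at the Date of Last Dose already collected on the End of Study eCRF.
- For subjects removed for missing more than 14 consecutive days, keep the date of discontinuation, state which field supplies it, and count the missed days as missed in the diary formula too.

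**Cost.** SAP wording and minor programming. The diary items that SAP 6.8 says are transcribed for compliance are missed-tablet totals, so the Part II first-dose date may need one added eCRF field.
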